3. SUBJECT SELECTION

3.1 Inclusion Criteria

To be included in this study, subjects should complete all screening procedures and meet all of the following criteria:

3.1.1 Willing and able to provide written informed consent and HIPAA authorization for the release of personal health information. A signed informed consent must be obtained before screening procedures are performed.

NOTE: HIPAA authorization may be either included in the informed consent or obtained separately.

3.1.2 Males 18 years of age and above

3.1.3 Body weight $> 30\text{kg}$

3.1.4 History of radical prostatectomy and/or primary radiation therapy to the prostate

3.1.5 Histologically confirmed prostate cancer with progressive disease defined as:

- Rising PSA (50% or more increase to a level of 0.50 ng/mL or more, based on at least 3 PSA determinations obtained at least 1 week apart). The 50% rise in PSA is across the 3 determinations, and these determinations do not need to be sequential.
- PSA doubling time of \leq 9months as calculated according to the Memorial Sloan Kettering Cancer Center nomogram
(<http://www.mskcc.org/mskcc/html/10088.cfm>)

3.1.6 No evidence of metastatic disease on conventional imaging (CT/MRI and bone scan). However, subjects with pelvic and/or retroperitoneal nodes $< 2\text{cm}$ in the short axis will be permitted on study, as they are considered not to have definitive metastases. (Note: *Metastatic disease on investigational imaging, Prostate Specific Membrane Antigen-targeted (PSMA) PET, PET-choline, or other novel PET tracers who do not have evidence of metastatic disease using conventional imaging (CT/MRI, bone scan) are allowed.*)

3.1.7 Molecular evidence of DDR deleterious mutations (somatic or germline), including BRCA1, BRCA2, ATM, CHEK1, CHEK2, FANCA, RAD51B, RAD51C, RAD51D, RAD54L, PALB2, BRIP1, BARD1, or CDK12. Mutations may be truncating, splice site mutations, missense or homozygous deletions. Mutation status is determined by a local laboratory with the result documented in the subject's medical record, previously obtained genomic testing from a CLIA-certified lab, or via archival or fresh tissue.

3.1.8 ECOG status of ≤ 1 (Appendix A: Performance Status Criteria)

3.1.9 Normal organ function with acceptable initial laboratory values within 14 days of treatment start:

WBC	³ 2000/ μL
ANC	³ 1500/ μL
Hemoglobin	³ 10g/dL
Platelet count	³ 100,000/ μL
Creatinine Clearance	$\geq 51 \text{ mL/min}$ estimated using the Cockcroft-Gault equation Estimated creatinine clearance = $\frac{(140 - \text{age [years]}) \times \text{weight (kg)}}{\text{serum creatinine (mg/dL)} \times 72}$
Bilirubin	$\leq 1.5 \text{ ULN}$ (unless documented Gilbert's disease)
SGOT (AST)	$\leq 2.5 \times \text{ULN}$ (unless liver metastases are present, in which case AST must be $\leq 5 \times \text{ULN}$)
SGPT (ALT)	$\leq 2.5 \times \text{ULN}$ (unless liver metastases are present, in which case ALT must be $\leq 5 \times \text{ULN}$)

3.1.10 Non-castrate level of testosterone defined as a value ³ 150 ng/dL

3.1.10 Life expectancy of ≥ 52 weeks.

3.1.11 Agree to use two medically acceptable, highly effective forms of birth control (e.g., spermicide in conjunction with a barrier such as a condom) or sexual abstinence for the duration of the study, including 180 days after the last dose of study drug. Sperm donation is prohibited during the study and for 3 months after the last dose of study drug.

Female partners of childbearing potential should use hormonal or barrier contraception unless postmenopausal or abstinent.

3.2 Exclusion Criteria

- 3.2.1 No other malignancy from which the subject has been disease-free for less than 3 years, with the exception of adequately treated and cured non-invasive malignancies such as basal or squamous cell skin cancer or superficial bladder cancer.
- 3.2.2 Less than one month prior to treatment start from last prior regimen or radiation exposure. Prior radiotherapy to the prostate (adjuvant or salvage radiotherapy) is allowed.
- 3.2.3 No prior investigational use with an anti-PD(1) including durvalumab or anti-CTLA4 antibody.
- 3.2.4 No prior treatment with a PARP inhibitor, including olaparib.
- 3.2.5 No concomitant or prior therapy with any of the following: IL-2, interferon, or other non-study immunotherapy regimens; immunosuppressive agents; or chronic use of systemic corticosteroids within 6 weeks of treatment start. Exceptions include: intranasal, inhaled, topical steroids, or local steroid injections (e.g., intra articular injection); Systemic corticosteroids at physiologic doses not to exceed 10 mg/day of prednisone or its equivalent; Steroids as premedication for hypersensitivity reactions (e.g., CT scan premedication)
- 3.2.6 No receipt of live attenuated vaccine within 30 days prior to treatment start *Note: enrolled subjects should not receive live vaccine while receiving IP and up to 30 days after the last dose of study therapy*
- 3.2.7 Concomitant use of known strong CYP3A inhibitors (e.g., itraconazole, telithromycin, clarithromycin, protease inhibitors boosted with ritonavir or cobicistat, indinavir, saquinavir, nelfinavir, boceprevir, telaprevir) or moderate CYP3A inhibitors (e.g. ciprofloxacin, erythromycin, diltiazem, fluconazole, verapamil). The required washout period prior to treatment start is 2 weeks.
- 3.2.8 Concomitant use of known strong (e.g., phenobarbital, enzalutamide, phenytoin, rifampicin, rifabutin, rifapentine, carbamazepine, nevirapine and St John's Wort) or moderate CYP3A inducers (e.g., bosentan, efavirenz, modafinil). The required washout period prior to starting olaparib is 5 weeks for enzalutamide or phenobarbital and 3 weeks for other agents.
- 3.2.9 More than 2 cycles of intermittent hormones for the treatment of biochemical recurrence, with a cycle defined as a period of consistent ADT (generally 3-12 months) followed by intentional cessation of ADT without re-initiation of ADT until the PSA rises. Prior ADT in the treatment of localized prostate cancer or with salvage radiation therapy is allowed. Prior use of abiraterone acetate with prednisone, enzalutamide, apalutamide, or other androgen receptor/androgen biosynthesis inhibitors are allowed if used in the localized or biochemically recurrent disease state provided that there was no evidence of disease progression while on these therapies.

- 3.2.10 No medical conditions such as uncontrolled hypertension, uncontrolled diabetes mellitus, cardiac disease that would, in the opinion of the investigator, make this protocol unreasonably hazardous.
- 3.2.11 Subjects considered a poor medical risk due to a serious, uncontrolled medical disorder or non-malignant systemic disease. Examples include, but are not limited to, uncontrolled ventricular arrhythmia, myocardial infarction within 3 months of treatment start, uncontrolled major seizure disorder, unstable spinal cord compression, superior vena cava syndrome, extensive interstitial bilateral lung disease on High Resolution Computed Tomography (HRCT) scan or any psychiatric disorder that prohibits obtaining informed consent.
- 3.2.12 No active infection including tuberculosis (TB) (clinical evaluation that includes clinical history, physical examination and radiographic findings, and TB testing in line with local practice), hepatitis B (known positive HBV surface antigen (HBsAg) result), hepatitis C, or active infection with human immunodeficiency virus (positive HIV 1/2 antibodies). Subjects with a past or resolved HBV infection (defined as presence of hepatitis B core antibody [anti-HBc] and absence of HBsAg) are eligible. Subjects positive for hepatitis C (HCV) antibody are eligible only if polymerase chain reaction is negative for HCV RNA
- 3.2.13 No autoimmune disease: subjects with a history of inflammatory bowel disease, including ulcerative colitis and Crohn's Disease, are excluded from this study, as are subjects with a history of symptomatic disease (e.g., rheumatoid arthritis, systemic progressive sclerosis [scleroderma], systemic lupus erythematosus, autoimmune vasculitis [e.g., Sarcoidosis syndrome or Wegener's granulomatosis with polyangiitis]); motor neuropathy considered of autoimmune origin (e.g., Guillain-Barre syndrome and myasthenia gravis); Graves' disease. Exceptions include history of eczema, vitiligo, alopecia, hypothyroidism (e.g., following Hashimoto syndrome), and any chronic skin condition that does not require systemic therapy; subjects without active disease in the last 5 years prior to treatment start may be included but only after consultation with the treating physician. Exceptions may be made on a case by case basis upon discussion with the Sponsor Principal Investigator.
- 3.2.14 No history of active primary immunodeficiency
- 3.2.15 No major surgery within 4 weeks of treatment start. Subjects must have recovered from any significant effects of any major surgery but investigators may discuss with the Sponsor Principal Investigator in the case of any exceptions.
- 3.2.16 No blood transfusion within 28 days of treatment start.
- 3.2.17 Resting ECG with QTc > 470 msec on 2 or more time points within a 24 hour period or family history of long QT syndrome
- 3.2.18 Enrollment in another clinical trial with a therapeutic agent. Subjects may co-enroll on investigational imaging studies (e.g., PSMA PET) or correlative trials.
- 3.2.19 No previous allogeneic bone marrow transplant or double umbilical cord blood transplant.
- 3.2.20 No history of leptomeningeal carcinomatosis

- 3.2.21 No unresolved toxicity (Common Terminology Criteria for Adverse Event (CTCAE) Grade \geq 2) caused by previous anticancer therapy, excluding alopecia, vitiligo, and the laboratory values described in the inclusion criteria. Subjects with Grade \geq 2 neuropathy will be evaluated on a case-by-case basis after consultation with the Sponsor Principal Investigator. Subjects with irreversible toxicity not reasonably expected to be exacerbated by treatment with study drugs may be included only after consultation with the Sponsor Principal Investigator.
- 3.2.22 No subjects who are HIV-positive on combination antiretroviral therapy because of the potential for pharmacokinetic interactions with olaparib. In addition, these subjects are at increased risk of lethal infections when treated with marrow suppressive therapy.
- 3.2.23 No subjects with baseline moderate to severe hepatic impairment (Child-Pugh Class B and C).
- 3.2.24 No subjects with myelodysplastic syndrome/acute myeloid leukemia or with features suggestive of MDS/AML.
- 3.2.25 No known allergy to any of the compounds under investigation or excipients of the product.
- 3.2.26 Subjects unable to swallow orally administered medication and subjects with gastrointestinal disorders likely to interfere with absorption of the study medication.
- 3.2.27 No other condition which, in the opinion of the investigator, would preclude participation in this trial.

4. ENROLLMENT PLAN

4.1 Enrollment Plan

4.1.1 *Anticipated Enrollment*

This study is anticipated to enroll 32 subjects.

4.1.2 *Recruitment*

Potential research subjects will be identified by a member of the subject's treatment team, the protocol investigator, or research team at participating centers from Medical Oncology, Radiation Oncology and Urology offices. Investigators will screen the subject's medical records for suitable research study subjects and discuss the study and their potential for enrolling in the research study.

4.2 Eligibility Confirmation

[figure not shown]
Confirmation of eligibility will be completed centrally by the PCCTC prior to treatment start. A record of subjects who fail to meet eligibility criteria (i.e., screen failures) will be maintained. A complete, signed informed consent and HIPAA authorization are required as part of eligibility confirmation. All subjects must sign an IRB-approved informed consent prior to starting any protocol-specific procedures; however, evaluations performed as part of routine care prior to informed consent can be used for screening and eligibility confirmation.

5. TREATMENT/INTERVENTION PLAN

This is a phase II, single arm, multi-center trial that will evaluate the combination of olaparib 300mg twice daily (600mg total daily dose) with durvalumab 1500mg IV monthly in biochemically recurrent castration sensitive prostate cancer. The trial will be conducted at sites who are members of the PCCTC Network.

As seen in the trial design (Figure 2), subjects will be treated concurrently with olaparib + durvalumab continuously for 24 months. After the first 4 months, if a subject fails to achieve an undetectable PSA with the combination of olaparib and durvalumab, ADT will be added for 6 months (starting at Cycle 5) while continuing treatment with olaparib and durvalumab. For subjects who have an undetectable PSA [PSA of <0.05 or PSA <0.10] for institutions where this is the lower limit of detection] after the first 4 months of treatment, they will continue on the combination of olaparib + durvalumab continuously for 24 months (without ADT). As long as it is believed that subjects are clinically benefiting, they will remain on treatment for up to 24 months with olaparib and durvalumab. For example, a subject with a PSA reduction that does not achieve an undetectable PSA would be allowed to remain on study for the duration of the trial. Subjects who meet progression criteria while on active therapy would come off of trial. If subjects respond and later progress in the one-year follow-up period (beyond 24 months), they will be allowed to be re-induced with the combination.

Figure 2. Study schema for olaparib and durvalumab in subjects with castration-sensitive prostate cancer (biochemical recurrence) harboring DNA damage repair mutations

DDR deleterious mutations (somatic or germline) will include BRCA1 (breast cancer susceptibility gene), BRCA2, ATM (ataxia telangiectasia mutated serine/threonine kinase), CHEK2, FANCA, RAD51C, RAD51D, PALB2, BRIP1, BARD1, and CDK12. Mutations may be truncating, splice site mutations, missense or homozygous deletions. Subjects will be allowed on trial using local testing, previously obtained genomic testing from a validated lab (e.g., expedited germline testing from Color), or via archival or fresh tissue.

The following assessments and procedures will occur during the study. A schedule of assessments is provided in Appendix B.

5.1 Study Procedures

5.1.1 Informed consent and research/HIPAA authorization

Before initiating any protocol-specific screening activities, the scope of the study should be explained to each subject. Subjects should be consented in accordance with Section 11.3 Written Informed Consent, including completion of a research/HIPAA authorization.

5.1.2 *Inclusion/exclusion criteria*

During the screening period, subject eligibility will be determined according to the inclusion and exclusion criteria (Sections 3.1 Inclusion Criteria & 3.2 Exclusion Criteria).

5.1.3 *Demographics and medical history*

Demographics and medical history collected will include:

- Date of birth (or age if date of birth is not allowed to be collected by local regulations)
- Significant past and ongoing conditions
- Dates of the primary prostatectomy and pathologic state
- Dates of prior radiation therapy
- Dates of prior hormonal therapies

5.1.4 *Concomitant medications*

Concomitant medications are permitted while on study if the medication is not expected to interfere with the evaluation of safety or efficacy, and is not otherwise restricted or prohibited (see Appendix C for a listing of medications with the potential for drug interactions).

5.1.5 *Vital signs, height, and weight*

Vitals will include temperature, blood pressure, and pulse. Height and weight will also be collected as described in Appendix B.

5.1.6 *Performance Status*

Performance status will be assessed using ECOG or Karnofsky scales (Appendix A).

5.1.7 *Physical examination*

A complete physical examination will be performed at screening. A symptom-directed physical exam may be performed at subsequent visits.

5.1.8 *Histologic and radiologic (per PCWG3 and RECIST 1.1 criteria) confirmation of disease*

Pathologic confirmation of prostate cancer and no evidence of metastasis on conventional CT or Bone Scan.

5.1.9 *Laboratory tests*

Laboratory tests will be performed by local labs and will include:

- CBC with differential: white blood cells count (WBC), red blood cell count (RBC), hemoglobin (HGB), hematocrit (HCT), platelet count (UNVPLT), neutrophils (NEUTP), lymphocytes (LYMP), monocytes (MONP), eosinophils (EOSP), basophils (BASOP)). If absolute differentials not available please provide % differentials.

- PSA
- Serum testosterone (TEST)
- Comprehensive Metabolic Panel (CMP): glucose (GLU), calcium (CA), albumin (ALB), total protein (TP), sodium (NA), potassium (K), bicarbonate (CO₂), chloride (CL), blood urea nitrogen (BUN), creatinine (CREAT), alkaline phosphatase (ALK), alanine transaminase (ALT), aspartate transaminase (AST), total bilirubin (TBILI)
- Thyroid function tests: TSH, free T4 and free T3
- Urinalysis: pH, specific gravity, hemoglobin, glucose, ketones, and protein by dipstick, with microscopic exam if any of the dipstick analytes are 2+ or higher.
- Coagulation Tests: Coagulation [activated partial thromboplastin time (APTT) and international normalized ratio (INR)] will be performed at baseline and if clinically indicated unless the subject is receiving warfarin. Subjects taking warfarin may participate in this study; however, it is recommended that prothrombin time (INR and APTT) be monitored carefully at least once per week for the first month, then monthly if the INR is stable. The reason(s) for the use, doses and dates of treatment should be recorded in the subject's medical records and appropriate section of the EDC.
- If clinically indicated, the investigator may order amylase and lipase
- Bone marrow or blood cytogenetic samples may be collected for subjects with prolonged hematological toxicities

These tests will be performed by the hospital's local laboratory. Additional analyses may be performed if clinically indicated.

Any clinically significant abnormal laboratory values should be repeated as clinically indicated and recorded on the CRF.

In case a subject shows an AST or ALT $\geq 3 \times \text{ULN}$ or total bilirubin $\geq 2 \times \text{ULN}$ please refer to Appendix C: 'Actions required in cases of combined increase of aminotransferase and Total Bilirubin – Hy's Law', for further instructions

5.1.10 ECG

All ECGs should be 12-lead ECGs performed in a supine position. ECGs should be performed prior to drawing blood when possible. An ECG is required prior to starting study treatment and when clinically indicated.

Twelve-lead ECGs will be obtained after the subject has been rested in a supine position for at least 5 minutes in each case. ECGs will be recorded at 25 mm/sec. All ECGs should be assessed by the investigator as to whether they are clinically significantly abnormal / not clinically significantly abnormal. If there is a clinically significant abnormal finding, the site will record it as an AE on the eCRF. The original ECG traces must be stored in the subject medical record as source data.

5.1.11 Computerized tomography (CT) or magnetic resonance imaging (MRI)

Radiographic evaluations will include CT of the chest, abdomen, and pelvis with contrast or MRI with contrast of the abdomen and pelvis, and CT chest without contrast. The method of assessment and techniques while on study should be the same as used at baseline.

5.1.12 Radionuclide bone scan

Radionuclide bone scanning (whole body) should be performed using 99mTc-methylene.

5.1.13 Select PRO – CTCAE

Designed to assess potential drug toxicity from the patient perspective (Appendix F)

5.2 Correlative/Special Studies

5.2.1 Blood Biomarkers: PBMCs and serum will be collected while on trial for future investigation of immune correlates. This may include evaluation of T-cell subsets and immunophenotyping, functional status of T effector cells, multiplex cytokine analysis, tumor associated antigens; cfDNA will also be collected for potential future use.

5.2.3 PDL-1 Expression: PDL-1 expression may be performed in the future using archival prostatectomy or prostate biopsy tissue.

5.2.4 Next generation sequencing and analysis of mutational load, immune driver genes, activation of the cyclic GMP-AMP synthase (cGAS)-Stimulator of Interferon Genes (STING) pathway, and immune microenvironment characterization may be performed using archived prostatectomy or prostate biopsy tissue.

5.2.5 As part of eligibility to determine if a subject has a DNA Damage Repair alteration, a matched normal control sample (e.g., blood or saliva) may be required dependent upon the assay being utilized. MSK-IMPACT requires a normal control blood sample while Tempus uses a saliva sample.

5.3 Follow-up (Every 12 weeks)

Subjects will be followed per the schedule in Appendix B. Subjects withdrawn from the study because of AEs will be followed until the adverse event has either resolved or stabilized. Reasons for premature withdrawal should be determined and noted.

5.4 Dose Modifications

If subject requires that the study drug be discontinued because of an adverse event (as described below) or have a treatment interruption of greater than 8 weeks for olaparib or 8 weeks for durvalumab, at the investigator's discretion, they may continue on the other agent alone until progression. Refer to Appendix G and Appendix H for management of toxicities.

5.4.1 Durvalumab Dose Modification

Dose reductions for durvalumab are not permitted. For dose modification and toxicity management guidelines for durvalumab, refer to Appendix G.

5.4.2 *Olaparib dose levels*

Dose Level	Olaparib
Level 0	300 mg BID
Level -1	250 mg BID
Level -2	200 mg BID
Level -3	Discontinue

Subjects requiring more than two dose reductions will have to discontinue olaparib. 100 mg and 150 mg tablets will be supplied for olaparib.

5.4.3 *Toxicities that require discontinuation from study treatment*

Protocol therapy should be discontinued if a subject experiences:

- Any CTCAE Grade 4 toxicity with the exception of:
 - CTCAE Grade 4 neutropenia of 5 days or fewer duration
 - CTCAE Grade 4 nausea/vomiting or diarrhea that resolves to Grade 3 or less within 72 hours
 - CTCAE Grade 4 laboratory abnormalities that can be readily corrected with 72 hours and do not result in hospitalization.
- CTCAE Grade 3 thrombocytopenia with hemorrhage
- CTCAE Grade 3 febrile neutropenia
- Hy's Law (AST or ALT >3x ULN with concomitant serum bilirubin >2x ULN and no alternate etiology)
- Bone marrow findings consistent with myelodysplastic syndrome (MDS)/acute myeloid leukemia (AML)

5.5 **Concomitant Medications and Supportive Care**

Because of the potential for drug-drug interaction, the concurrent use of all other drugs, over-the-counter medications, and alternative therapies must be documented on the eCRF.

Subjects should not donate blood while participating in this study or for at least 90 days following the last infusion of durvalumab or olaparib.

Refer to Appendix D for more information on concomitant medications and supportive care guidance.

5.6 **Other Concomitant Treatment**

Any medications, with the exceptions noted in Appendix D, which are considered necessary for the subject's welfare, and which it is believed will not interfere with the study medication, may be given at the discretion of the Investigator, providing the medications, the doses, dates and reasons for administration are recorded in the EDC.

In addition, any diagnostic, therapeutic or surgical procedure performed during the study period must be recorded in the EDC.

All medications (prescriptions or over-the-counter medications) continued at the start of the trial (from the time of informed consent) or started during the study or until 30 days from the end of the last protocol treatment and different from the study medication must be documented.

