APPENDIX H. DOSE MODIFICATION AND TOXICITY MANAGEMENT GUIDELINES FOR OLAPARIB

Olaparib dose reductions based on hematologic nadir

Granulocytes and Platelets	Olaparib Dose Adjustment
ANC < LLN* but \geq 1000/mm3 and/or PLT < LLN but \geq 50,000/mm3 (CTCAE Grade 1-2)	Investigator judgment to continue study treatment in full dose or if dose interruption, this should be for a maximum of 4 weeks; appropriate supportive treatment and causality investigation
ANC < 1000/mm3 and/or PLT < 50,000/mm3 (CTCAE Grade 3 - 4)	Hold olaparib. Once toxicity resolves to Grade 1, olaparib may be continued -1 dose level.

*LLN = lower limit of normal

- If the ANC nadir is under 1000/mm3 (CTCAE Grade 3 - 4) and/or the platelet nadir is under 50,000/mm3 (CTCAE Grade 3 - 4) after a 1 dose level reduction of olaparib, then the next cycle will be started at -2 dose level once toxicity resolved to CTCAE Grade 1 or better
- Subjects requiring more than two dose reductions will discontinue olaparib

Management of toxicity related to olaparib

Any toxicity observed during the course of the study could be managed by interruption and/ or dose reduction of the dose if deemed appropriate by the Investigator. Olaparib must be interrupted until the subject recovers completely or the toxicity reverts to the NCI-CTCAE Grade 1 or less. If olaparib is delayed more than 8 weeks for any reason, or if a dose reduction below 200 mg daily is required, subjects will discontinue treatment with olaparib.

- Where toxicity reoccurs following re-challenge with olaparib, and where further dose interruptions are considered inadequate for management of toxicity, then the subject should be considered for dose reduction or must permanently discontinue treatment with olaparib.
- Treatment must be interrupted if any NCI-CTCAE Grade 3 or Grade 4 AE occurs which the Investigator considers to be related to administration of olaparib.

Adverse Event with Possible Relationship to Olaparib	Action to Take

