Non-hematologic toxicities including nausea, vomiting, and diarrhea	Grade 1 and Grade 2 If subjects develop intolerable Grade 1 or Grade 2 toxicities (per subject) then they can undergo a dose reduction. For Grade 4 toxicities despite optimal medical therapy, hold olaparib until equal or under Grade 1. Resume at one dose level reduction. Events of nausea and vomiting are known to be associated with olaparib treatment. In study, they are generally mild to moderate (CTCAE Grade 1 or Grade 2) severity, intermittent and manageable on continued treatment. The first onset generally occurs in the first month of treatment with the incidence of nausea and vomiting not showing an increase over the treatment cycles.

		No routine prophylactic anti-emetic treatment is required at the start of study treatment; however, subjects should receive appropriate anti-emetic treatment at the first onset of nausea or vomiting and as required thereafter, in accordance with local treatment practice guidelines
General non-hematologic toxicities excluding nausea, vomiting, and diarrhea	Grade 3 or higher toxicities	Delay until recovery to Grade 1 or lower and reduce one dose level to 250mg BID). A maximum of 2 dose reductions can be made for repeat toxicity.
Anemia	CTCAE Grade 1 or Grade 2 (Hemoglobin (Hb) > 8 g/dl)	Investigate and manage as deemed appropriate by the investigator with or without interruption of study drug or change in dose, taking into account previous history of anemia. Common treatable causes of anemia (e.g., iron, vitamin B12 or folate deficiencies and hypothyroidism) should be excluded. In some cases, management of anemia may require blood transfusions.
	CTCAE Grade 3 (Hb < 8g/dl) or worse	
Study treatment should be interrupted for up to maximum of 4 weeks to allow for bone marrow recovery and the subject should be managed appropriately. Study treatment can be restarted at the reduced dose if Hb has recovered to > 10 g/dl. Any subsequently required anemia related interruptions, considered likely to be dose related, or coexistent with newly developed neutropenia, and or thrombocytopenia, will require a further study treatment dose reduction to 200 mg BID.
 
If a subject has been treated for anemia with multiple blood transfusions without study treatment interruptions and becomes blood transfusion dependant as judged by investigator, study treatment should be permanently discontinued.

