Neutropenia and leukopenia	CTC Grade 3 or worse neutropenia occurs	
Manage as deemed appropriate by the investigator with close follow up and interruption of study drug. Primary prophylaxis with Granulocyte colony-stimulating factor (G-CSF) is not recommended, however, if a subject develops febrile neutropenia, study treatment should be stopped and appropriate management including G-CSF should be given according to local hospital guidelines. Please note that G-CSF should not be used within at least 24 h of the last dose of study treatment.
 
Study treatment can be restarted at the same dose if an AE of neutropenia or leukopenia have been recovered up to CTC AE Grade less than or equal to Grade 1 (ANC > 1.5 x 10⁹/L). Growth factor support should be stopped at least 24h before restarting study drug (7 days for pegylated G-CSF).
 
Any subsequent interruptions will require study treatment dose reductions to 250 mg BID as a first step and to 200 mg

		BID as a second step for a 300 mg monotherapy starting dose
Thrombocytopenia	CTCAE Grade 3 or worse	
Study treatment should be interrupted for a maximum of 4 weeks. In some cases, management of thrombocytopenia may require platelet transfusions. Platelet transfusions should be done according to local hospital guidelines.
 
Any subsequent interruptions will require study treatment dose reductions to 250 mg BID as a first step and to 200 mg BID as a second step for a 300 mg monotherapy starting dose

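### Section 5.4.3 stops protocol therapy after most Grade 4 toxicities, but Appendix H has olaparib resumed after some of the same events, and no sentence says which text governs

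*Combined protocol and SAP*

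**What the plan says.** Section 5.4.3 lists the toxicities for which protocol therapy should be discontinued. The first entry is "Any CTCAE Grade 4 toxicity with the exception of" three cases:

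- neutropenia lasting no more than 5 days;
- nausea, vomiting or diarrhea that comes down to Grade 3 or below within 72 hours;
- laboratory abnormalities readily corrected within 72 hours and not leading to admission.

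Section 5.4, which introduces it, tells sites: "Refer to Appendix G and Appendix H for management of toxicities". It also says that when one drug is discontinued or long interrupted, at the investigator's discretion "they may continue on the other agent alone until progression".

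Appendix H gives these instructions for olaparib:

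- General non-hematologic toxicity other than nausea, vomiting and diarrhea, Grade 3 and above: "Delay until recovery to Grade 1 or lower and reduce one dose level to 250mg BID".
- Nausea, vomiting and diarrhea: "For Grade 4 toxicities despite optimal medical therapy, hold olaparib until equal or under Grade 1. Resume at one dose level reduction".
- Neutrophil or platelet nadir, Grade 3 to 4: "Once toxicity resolves to Grade 1, olaparib may be continued -1 dose level".
- Neutropenia and leukopenia, Grade 3 or worse: "Study treatment can be restarted at the same dose if an AE of neutropenia or leukopenia have been recovered".
- Anemia, Grade 3 or worse: "Study treatment can be restarted at the reduced dose if Hb has recovered to > 10 g/dl".

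None of these rows repeats the 5-day, 72-hour or no-admission limits of 5.4.3.

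**The concern.** A site that follows Appendix H to the letter would give olaparib again to a man whom 5.4.3 says must stop. Section 5.4 cites the appendix without ranking it below the body text, so both texts are live instructions. The trial is multi-center, and its men have no metastases on conventional imaging. Section 1.2.10 counts observation among the options for such men. Whether one of them is re-exposed after a Grade 4 event should rest on a single rule that every site applies in the same way.

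**Working it through.** This is a comparison of texts, so the main check sets the two rules side by side for each kind of Grade 4 event.

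| Grade 4 event | Section 5.4.3 | Appendix H | Conflict? |
|---|---|---|---|
| Clinical non-hematologic event other than nausea, vomiting, diarrhea | Discontinue; no exception applies | Delay, then 250 mg BID | Always |
| Nausea, vomiting, diarrhea | Discontinue unless at Grade 3 or below within 72 hours | Hold, then one level down; no time limit | Only if it lasts beyond 72 hours |
| Neutrophils (nadir table and neutropenia row) | Discontinue unless it lasts 5 days or fewer, or the laboratory exception is met | Resume one level down (table) or at the same dose (row) | Only outside an exception |
| Platelets (nadir table) | Discontinue unless the laboratory exception is met | Resume one level down | Only outside the exception |
| Anemia | Discontinue unless the laboratory exception is met | Restart at a reduced dose once hemoglobin recovers | Only outside the exception |

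Four remarks on the table:

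1. A non-hematologic laboratory value in the first row could still meet the third exception. That is why *always* is confined to clinical events.
2. The separate thrombocytopenia row is not counted. It speaks of interruption for up to 4 weeks and only implies a restart.
3. It does not matter whether *protocol therapy* in 5.4.3 means both drugs or only the drug held responsible. Appendix H deals with events possibly related to olaparib, and on either reading 5.4.3 would stop olaparib for such an event.
4. Appendix H gives two restart doses after Grade 3 to 4 neutropenia, which suggests that its parts were not reconciled with one another.

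Next, is there a rule of precedence? Appendix G calls its content guidelines and expressly not mandates. Appendix H has *guidelines* in its title but carries no such disclaimer. It says treatment must be interrupted (not discontinued) for a Grade 3 or 4 event related to olaparib. Section 7.1.10 says the Appendix H guidance will be applied in suspected pneumonitis. No sentence ranks 5.4.3 above Appendix H.

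Last, the plan's own figures. Section 10.2 stops the trial at 4 toxicities in 8 men, 5 in 16, 7 in 24 or 9 in 32. Let d(k) be the probability of k toxicities without having crossed. Each block of 8 men adds x toxicities with probability C(8,x) p^x (1−p)^(8−x), and mass at or above the boundary is moved to *crossed*. The cumulative crossing probabilities are:

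| Rate p | 8 men | 16 men | 24 men | 32 men | Plan |
|---|---|---|---|---|---|
| 0.15 | 0.0214 | 0.0841 | 0.1031 | 0.1123 | 0.11 |
| 0.35 | 0.2936 | 0.7168 | 0.8323 | 0.8922 | 0.89 |

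Both printed values reproduce.

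**The case against.** The strongest answer is that the texts can be read together. The heading of 5.4.3 speaks of toxicities that require discontinuation, and 5.4 points to discontinuation as described further on. Appendix H opens its management section permissively, leaving interruption or reduction to the investigator's view. Appendix G also says to discontinue for Grade 4 non-immune events, apart from laboratory values, which it leaves to judgment. On this reading 5.4.3 is the outer limit and Appendix H works inside it. This is the likelier intention, and it narrows the problem. It does not remove it, because the general non-hematologic row is a plain instruction covering Grade 4 and the reader has to infer the ranking.

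The risk is also bounded, and this stands:

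- The general non-hematologic, nausea/vomiting/diarrhea and nadir rules require recovery to Grade 1 before olaparib resumes.
- A delay of more than 8 weeks ends olaparib.
- Section 5.7 lets the treating physician stop when retreatment would be dangerous.
- Serious events go to the coordinating center within 24 hours and are reviewed by the Sponsor Principal Investigator.
- Section 1.2.5 describes the common non-hematologic toxicities of olaparib as generally Grade 1 or 2.

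These safeguards limit harm, but they do not tell a site which dosing rule applies.

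A reader might go further and infer that the conflict undermines the toxicity stopping rule, because 10.2 counts non-immune toxicity only when it requires *trial discontinuation*. The documents do not support that step. Section 10.2 leaves the term undefined but never refers to 5.4.3, and the printed probabilities are right for any fixed definition.

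**Conclusion.** The contradiction is in the text and should be corrected. It is unavoidable in one Appendix H row, for every Grade 4 clinical event in it. In the nausea/vomiting/diarrhea, nadir, neutropenia and anemia parts it arises only when no 5.4.3 exception is met. The consequence is that re-exposure to olaparib after a Grade 4 event can differ by site.

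No expected number of men can be given, because the documents state no Grade 4 rate. Nothing shows that sites have acted differently or that any man was wrongly re-exposed. No effect on the primary endpoint is claimed. The conclusion assumes only that sites read Appendix H as applicable instruction, which 5.4 invites.

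**What to change.** 1. Add to Section 5.4: *For Grade 4 events, Section 5.4.3 governs over Appendices G and H.*
2. In Appendix H, limit hold-and-resume to Grade 3 events and to Grade 4 events that meet a 5.4.3 exception. Otherwise discontinue.
3. If the sponsor wants treatment resumed after other Grade 4 events, list them as further exceptions in 5.4.3. One candidate is an endocrinopathy controlled on hormone replacement, after which Appendix G allows treatment to resume.

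The cost is a wording amendment, with no change to visits, data collection, boundary or sample size. The downside is that a few men who could have resumed under Appendix H will stop olaparib. Step 3 lets the sponsor decide where that is too strict.

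Separately, the sponsor could be asked whether *trial discontinuation* in 10.2 means stopping one drug or both. No default is proposed here, because a broad one could widen the counted event. If the counted rate rose from 0.15 to an assumed 0.17 or 0.20, the chance of stopping would go from 0.11 to 0.18 or 0.30 by the same recursion.
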